## 10.4 Treatment Compliance and Exposure

Duration of exposure, number of days dosed, compliance and drug holiday duration will be tabulated descriptively as per CRF response for safety population, by treatment and overall. This summary will be produced for each disease type and AChEI usage within disease type.

Duration of exposure for the treatment will be calculated as follows:

Duration of exposure in days = (Last dose date - First dose date) + 1

Duration of exposure also will be categorized as:

- i) 0 to 2 weeks
- ii) >2 to 6 weeks
- iii) >6 to 12 weeks
- iv) >12 to 16 weeks
- v) >16 to 20 weeks
- vi) >20 to 26 weeks
- vii) >26 weeks

Drug compliance will be categorized as:

- i) < 80%
- ii) >=80%

# 10.5 Efficacy

Summary statistics will include change from baseline comparison of ATH-1017 with placebo using a two-sample t-test without baseline adjustment. All statistical tests will be carried out using a one-sided 2.5% significance level and all comparisons will be reported with 95% confidence intervals for mITT population unless otherwise stated. The comparison between ATH-1017 (40 mg and 70 mg pooled) and placebo will serve as the primary efficacy comparison. This summary will be produced for each disease type and AChEI usage within disease type also.

Confidential Page 35 of 57

No adjustments will be made for multiple comparisons.

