## 7.1.2 Modified Intent-to-Treat (mITT) Population

The modified intent-to-treat (mITT) population will include all randomized subjects who took at least one dose of the study medication and who completed both an ADAS-Cog13 and ERP P300 assessment at Baseline and during at least one post-baseline visit. Subjects will be analyzed according to the dose they were randomized to.

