# 8 CHANGES IN CONDUCT OR PLANNED ANALYSES FROM THE PROTOCOL

The following changes have been made in the analytical strategies:

Since the study is stopped early, minimal analyses will be performed.

- No interim analysis will be performed.
- Alternate statistical comparison tests can be implemented as appropriate.
- No statistical conclusion can be made based on the statistical test, if generated.
- Other than summary statistics, all exploratory and subgroup analysis are optional.

Confidential Page 30 of 57

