#### 9.2 Baseline Definition

For safety summaries, the last pre-randomization measurement is defined as the baseline value. For clinical effect measures baseline is defined as the last pre-randomization measurement.

GST score, ADCS-CGI-C, and CaGI-C are change scores, so no further calculation is required. Appendix 1 describes calculation of the baseline GST score for baseline covariate purposes. For all other efficacy measures, baseline is the average of all measurements prior to first dosing, or if only one measurement exists that value will be used.

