#### 10.5.1 Primary Analysis

NOTE: The following description for the primary analysis was prepared to implement the intention of the protocol, however in view of the early stopping of the trial this analysis will not be performed, unless the simple summary statistics suggest a finding of interest, in which case this would be performed as an exploratory analysis.

The primary analysis will use a mixed model with repeated measures (MMRM) to compare the GST score between ATH-1017 and placebo at 26 weeks. In this MMRM model, GST score (a composite of the standardized change from baseline variables) will be considered as the outcome variable and the following fixed terms: baseline value, treatment arm, visit, treatment by visit interaction, baseline by visit by treatment interaction, GBA genotype, and baseline age. The correlations among repeated observations within a patient will be accounted for by specifying an unstructured covariance matrix. The least squares mean, and treatment differences will be estimated from the MMRM model.

The MMRM model summary will contains LSMEAN, Standard Error (SE), 95% CI at each visit by treatment (ATH-1017, Placebo) will be displayed. Also, LSMEAN for ATH-1017 difference from placebo, SE, 95% CI, and p-value at Week 26.

If convergence not met for the MMRM model, GST score between ATH-1017 and placebo at Week 26 will be compared using one sided t-test 2.5% significance level.

Additionally, the GST score will be listed and summarized for all visits. This summary will be produced for each disease type and AChEI usage within disease type also. A line plot with mean GST score and 95% CI over visit by treatment arm (40 mg ATH-1017, 70 mg ATH-1017 and placebo) will be displayed.

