## 10.5.2 Secondary Analysis

NOTE: The following description for the secondary analyses was prepared to implement the intention of the protocol, however in view of the early stopping of the trial this analysis will not be performed, unless the simple summary statistics suggest a finding of interest, in which case these would be performed as exploratory analysis.

The separate key secondary variables ADAS-Cog13 and ERP P300 latency will be analyzed using the MMRM model. Change form baseline ADAS-Cog13 score and change form baseline ERP P300 latency will be used as the outcome variable and the following fixed terms: baseline value, treatment arm, visit, treatment by visit interaction, baseline by visit by treatment interaction, GBA genotype, and baseline age. in the MMRM model. Similar summary statistics will be presented that was used for analysis of the primary endpoint. If MMRM model do not converge, active treatment and placebo groups will be compared using one sided t-test 2.5% significance level at Week 26 for change for baseline secondary variables.

Confidential Page 37 of 57

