## 10.5.6 Final Analysis

This is an early closure study; other than summary statistics, all analyses are optional.

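### The primary efficacy comparison and the MMRM fallback leave out baseline values already collected, and the SAP defines baseline in two ways; fix one definition and add an exploratory ANCOVA

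*SAP*

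**What the plan says.** Because the trial stopped early, SAP 6 labels efficacy exploratory and SAP 8 limits the work to minimal analyses. SAP 10.5 then specifies, within the summary statistics, a "change from baseline comparison of ATH-1017 with placebo using a two-sample t-test without baseline adjustment". It names pooled 40 mg and 70 mg against placebo as the primary efficacy comparison, at one-sided 2.5% with 95% confidence intervals. SAP 10.5.6 adds that "other than summary statistics, all analyses are optional", so this is the one efficacy comparison not made optional. SAP 8 softens that a little: "No statistical conclusion can be made based on the statistical test, if generated". Another bullet there permits other comparison tests but names none.

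The fallbacks are t-tests too. For the GST: "If convergence not met for the MMRM model, GST score between ATH-1017 and placebo at Week 26 will be compared using one sided t-test". For ADAS-Cog13 and P300: "If MMRM model do not converge, active treatment and placebo groups will be compared using one sided t-test". The models they replace list the baseline value as a fixed term, and so does the MMRM in protocol 8.3.1.

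The baseline data exist. Entry to the mITT population requires an ADAS-Cog13 and a P300 "assessment at Baseline and during at least one post-baseline visit". A composite baseline is derived as well: "Appendix 1 describes calculation of the baseline GST score for baseline covariate purposes".

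SAP 9.2 gives two definitions. One reads "For clinical effect measures baseline is defined as the last pre-randomization measurement", as does protocol 8.2. The other, for efficacy measures that are not themselves change scores, is the mean of all values before first dosing.

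**The concern.** Subtracting baseline is not the same as adjusting for it. A change score fixes the slope of follow-up on baseline at 1. When the true slope is lower, part of the baseline variation stays in the estimate and widens the interval. ANCOVA estimates the slope and removes that part, at the price of one degree of freedom. Here the covariate is collected, and for the GST specially derived, yet the comparison most readers will see does not use it, and the fallback loses the baseline term that its own model carried.

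The two baseline definitions raise a separate question. ADAS-Cog13 is scheduled once before dosing, so the definitions agree for it. P300 is recorded at Visit 2a and again pre-dose at Visit 2b. One definition picks a single recording and the other averages both, so the P300 change differs, and with it the GST. Two programmers following the SAP could report different numbers.

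At stake is the precision and reproducibility of the pooled estimate and its interval, not a confirmatory decision.

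**Working it through.** **Inputs from the documents.** The plan is 25 per arm (SAP 6.1.2), hence 25 placebo v 50 pooled active. The only sample-size arithmetic is 3 × 25 = 75; no formal calculation was made, so there is no power figure to reproduce. P300 is recorded twice before dosing (SAP Appendix 2), and pre- and post-dose P300 values in a window are averaged (SAP 9.6).

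**Assumptions.** The correlation ρ (0.5 to 0.9), the SDs and the achieved sizes (10 v 20, 5 v 10, 4 v 8) are not in the documents.

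**Step 1: one measure, equal SDs.** The change has variance 2(1−ρ)σ² and the ANCOVA residual (1−ρ²)σ², a ratio of (1+ρ)/2. Estimating the slope multiplies the ANCOVA variance by about 1+1/(N−4), which is 1.014 at N = 75 and 1.038 at N = 30.
- 25 v 50, ρ = 0.5: √(0.75 × 1.014) = 0.872, 13% narrower. ρ = 0.9: √(0.95 × 1.014) = 0.981, 2% narrower.
- 10 v 20, ρ = 0.5: √(0.75 × 1.038) = 0.882, 12% narrower. ρ = 0.9: √(0.95 × 1.038) = 0.993, about 1% narrower.

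Simulation (60,000 trials per setting) agrees, with 95% interval coverage of 94.7–95.2% for both methods.

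**Step 2: unequal SDs.** With k = follow-up SD / baseline SD, the large-sample ratio is k²(1−ρ²)/(1+k²−2kρ). At k = 1.25 and ρ = 0.8 the slope kρ is 1 and the ratio is 0.5625/0.5625 = 1. ANCOVA then gains nothing, and its interval is 0.7% wider at 25 v 50 and 2% wider at 10 v 20. At k = 0.8 the simulated variance ratios are 0.58–0.65 and 0.59–0.66.

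**Step 3: the two P300 baselines.** Take 10 v 20, each recording with variance 1 and any two recordings in a subject correlated 0.5. Follow-up is a mean of two, with variance 0.75, and 1/10 + 1/20 = 0.15.
- t-test, one baseline recording: √[(0.75+1−1) × 0.15] = 0.335
- t-test, averaged baseline: √[(0.75+0.75−1) × 0.15] = 0.274
- ANCOVA, one recording: √[(0.75−0.25) × 0.15 × 1.038] = 0.279
- ANCOVA, averaged: √[(0.75−0.25/0.75) × 0.15 × 1.038] = 0.255

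Choosing the averaged baseline alone cuts the t-test SE by 18% (0.274/0.335 = 0.82). ANCOVA then adds a further 7% (0.255/0.274 = 0.93).

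**Step 4: GST with averaged P300.** Assume uncorrelated measures and equal single-recording SDs. The absolute correlation of change with baseline is √[(1−ρ)/2] for ADAS-Cog13 and √[(1−ρ)/(2(1+ρ))] for P300. For the GST and its baseline it is the mean of the two.
- ρ = 0.5: mean of 0.500 and 0.408 is 0.454, and 1−0.454² = 0.794. The interval ratio is √(0.794 × 1.014) = 0.897 at 25 v 50 and √(0.794 × 1.038) = 0.908 at 10 v 20.
- ρ = 0.9: mean of 0.224 and 0.162 is 0.193, and 1−0.193² = 0.963. The ratios are 0.988 and 1.000.

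Percent narrowing of the 95% interval (negative means wider). The GST row at 25 v 50 is from the formula; the other rows are simulated.

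| | ρ 0.5 | 0.7 | 0.8 | 0.9 |
|---|---|---|---|---|
| One measure, 25 v 50 | 13 | 7 | 4 | 2 |
| One measure, 10 v 20 | 12 | 6 | 3 | 0.5 |
| GST, 25 v 50 | 10 | 5 | 3 | 1 |
| GST, 10 v 20 | 9 | 4 | 2 | 0 |
| GST, 5 v 10 | 5 | 1 | −2 | −4 |
| GST, 4 v 8 | 3 | −2 | −4 | −6 |

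In strata of 7 subjects, simulation for one measure gives an ANCOVA interval 5–21% wider at k = 1 or 1.25 and 3–9% narrower at k = 0.8.

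**The case against.** The SAP is open about what it does. It says the test is unadjusted, gives early stopping as the reason, rules out statistical conclusions and permits other tests, so ANCOVA is not barred. The t-test is valid over randomisation and its interval already covers chance baseline imbalance; imbalance is the same precision loss seen from another side, not a second harm. The derived baseline GST belongs to the optional MMRM, so leaving it out of a descriptive test breaks no rule, and for ADAS-Cog13 and P300 the unused covariate is simply the observed baseline. The planned 25 v 50 describes a trial that was not completed, and the mITT definition needs only one post-baseline visit, so Week 26 numbers may be lower still. Averaging P300 also shrinks what ANCOVA can add.

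All of that stands, and it limits the point to a modest, size-dependent gain. It does not remove it. A general permission to use other tests names no adjusted analysis and leaves the choice until data have been seen. Nor does any of it settle the two baseline definitions, which matter whichever test is used.

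**Conclusion.** The point holds as a low-cost improvement in precision and a wording conflict to resolve. At about 30 subjects or more, with equal SDs, ANCOVA narrows the interval by roughly 0% to 13% depending on correlation and measure. At 15 or 12 subjects the GST interval may narrow by 5% or widen by 6%. These ranges rest on assumed correlations, SDs and sizes, and the gain disappears when the slope is near 1. The conflict in SAP 9.2 needs no assumption: the definitions differ for P300 and therefore for the GST.

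A reader might infer more, but the documents do not support it:
- That the t-test is biased or could lead to a wrong decision. Randomisation keeps it valid, and SAP 6 and 8 make efficacy exploratory and rule out conclusions.
- That the SAP contradicts itself by deriving a covariate it does not use. The covariate serves the MMRM.
- That ANCOVA is better at any size. In very small samples it can be worse.
- That running the MMRM only if the summary statistics look interesting undermines the plan. That condition is stated openly for an exploratory analysis, no size can be attached to it, and it is not part of this point.

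**What to change.** 1. In SAP 9.2, keep one baseline definition and use it for both the change and the covariate, including baseline GST. The purpose given in protocol 3.1 for the extra pre-baseline P300 recording, reducing baseline variability, fits the average. Since protocol 8.2 uses the last value, record that choice in SAP 8 as a change.
2. In SAP 10.5, for the overall pooled comparison, and as the fallback in 10.5.1 and 10.5.2, add an ANCOVA of the change (or GST) on treatment and that measure's own baseline (baseline GST for the GST). Label it exploratory, show it beside the unadjusted t-test and report it whatever it shows.
3. If the overall Week 26 sample is 15 or fewer, treat the ANCOVA as supportive only. Use the t-test alone in the small disease-type and AChEI strata.

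The cost is SAP wording and one degree of freedom, with no new data. If the slope is near 1, the interval is about 2% wider at 10 v 20; smaller samples can cost more, as the table shows.

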### 8.3 Clinical Effect Analyses

## 8.3.1 Primary Clinical Effect Analysis - GST

The primary hypothesis is that treatment with ATH-1017 will result in a statistically significant reduction in change from baseline in the GST score (O'Brien, 1984) (combining the ADAS-Cog13 score and the change from baseline in ERP P300 at Week 26) relative to the placebo group in the mITT population. The primary analysis will test the statistical hypothesis of no difference between placebo and 70 mg ATH-1017 first and then 40 mg ATH-1017 versus placebo.

The primary analysis will use a mixed model with repeated measures (MMRM) to compare the estimated change from baseline between active treatment and placebo in the GST score. This analysis will assess whether or not there is a difference in estimated GST values between treatment groups and placebo at 26 weeks using least squares means estimates from the MMRM model, and will include terms for baseline, baseline by time interaction, and baseline by time by treatment interaction in the model. Additional terms will be included for GBA genotype, and site (with smaller sites grouped), and age. Least squares means and standard errors will be estimated from the MMRM model at Week 26. Further details relating to the primary analysis will be described in the SAP.

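### The SAP's primary efficacy contrast pools the two doses, while the protocol tests 70 mg and then 40 mg against placebo; the change is not listed, and no dose-versus-placebo difference with a CI is specified

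*SAP*

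**What the plan says.** **Protocol.** Section 8.3.1 says the primary analysis tests the hypothesis of "no difference between placebo and 70 mg ATH-1017 first and then 40 mg ATH-1017 versus placebo". That is two dose-specific contrasts in a stated order. Section 3 calls the study dose-ranging, and Section 3.2 says the doses studied are to support the choice of a dose for registration.

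**SAP, contrast.** Section 10.5 states: "The comparison between ATH-1017 (40 mg and 70 mg pooled) and placebo will serve as the primary efficacy comparison". It describes the comparison to be run as a "change from baseline comparison of ATH-1017 with placebo using a two-sample t-test without baseline adjustment", adds that "All statistical tests will be carried out using a one-sided 2.5% significance level", and ends with "No adjustments will be made for multiple comparisons". The MMRM in Section 10.5.1 has the same two groups: the LS mean, SE and "95% CI at each visit by treatment (ATH-1017, Placebo) will be displayed", followed by one ATH-1017 minus placebo difference at Week 26. Appendix 1 derives the GST score with two arms only, placebo and ATH-1017.

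**SAP, what remains by dose.** Section 9.1 presents efficacy summaries by treatment group. Section 10.5.1 plots mean GST with a 95% CI over visits for 40 mg, 70 mg and placebo separately.

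**SAP, list of changes.** Section 8 opens "The following changes have been made in the analytical strategies" and gives four bullets: no interim analysis; alternate comparison tests permitted; no statistical conclusion from any test; exploratory and subgroup analyses optional. Pooling is not among them. Section 10.5.1 says its text was "prepared to implement the intention of the protocol".

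**SAP, status.** Section 6 records that the study stopped early and that efficacy is exploratory. Section 10.5.1 runs the MMRM only if the simple summaries suggest something of interest. Section 10.5.6 makes everything beyond summary statistics optional.

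**The concern.** The groups being compared have changed, from each dose against placebo to both doses together against placebo. A reader who goes to SAP Section 8 to find departures from the protocol will not see this. A reader of 10.5.1 will be told that the two-group analysis is what the protocol intended.

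The practical loss is dose-specific information. With the interim comparison of the two doses also dropped (which Section 8 does list), the SAP names no estimated difference from placebo for either dose. If the two doses act differently, the pooled estimate averages them, and a signal at one dose is diluted by the other.

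**Working it through.** **1. The texts side by side**

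| Item | Protocol 8.3.1 | SAP 10.5, 10.5.1, Appendix 1 |
|---|---|---|
| Contrasts | 70 mg v placebo; 40 mg v placebo | pooled ATH-1017 v placebo |
| Order | 70 mg first, then 40 mg | none; no multiplicity adjustment |
| Listed in SAP Section 8? | – | no |
| Reason given? | – | none |

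The nearest Section 8 bullet, on alternate comparison tests, concerns which test is used. It does not say which groups are compared. Early stopping is given as the reason for not running the MMRM, never as the reason for pooling.

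**2. The plan's own figure.** The planned size is 75 evaluable subjects, 25 per arm (Protocol 8.6, SAP 6.1.2): 3 × 25 = 75, which agrees. Both documents say no formal calculation was made, so there is no stated effect, SD or power to reproduce.

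**3. Scale of the dilution (illustrative).** Inputs from the documents: 25 per arm and a one-sided 2.5% level. Assumed: SD = 1, so effects are in SD units, with a range of 0.5, 0.8 and 1.0.

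- Standard errors: single dose √(1/25 + 1/25) = 0.283 SD; pooled √(1/50 + 1/25) = 0.245 SD.
- If only one dose works with effect d, the pooled effect is d/2. At d = 0.8 the non-centrality is 0.8/0.283 = 2.83 (48 df) for that dose and 0.4/0.245 = 1.63 (73 df) pooled. The standardised signal falls to 1.63/2.83 = 58%.
- If both doses have effect d = 0.8, the pooled non-centrality is 0.8/0.245 = 3.27.

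Power from the non-central t distribution:

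| Assumed d | One dose v placebo | Pooled, one dose active | Pooled, both active |
|---|---|---|---|
| 0.5 SD | 41% | 17% | 52% |
| 0.8 SD | 79% | 36% | 90% |
| 1.0 SD | 93% | 52% | 98% |

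Mixing an active with an inactive dose also adds spread. At 0.8 SD this lowers the pooled figure by about 3 points (37% to 34% on a normal approximation).

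**4. Smaller enrolment.** SAP 9.5 and 10.5.1.1 say few subjects were enrolled but give no number. With 5 to 15 per arm (assumed) and 0.8 SD at one dose only, the same formula gives 20% to 56% for that dose and 10% to 24% pooled.

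**5. Width of the dose-level intervals at the planned size.** The half-width is 2.01 × 0.283 = 0.57 SD for one dose and 1.99 × 0.245 = 0.49 SD pooled.

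**The case against.** The strongest reply is that nothing confirmatory is left to protect. The study stopped early, the SAP bars statistical conclusions, the MMRM is skipped by default, and all efficacy analyses beyond summary statistics are optional. Power is a weak measure of harm for a test from which nothing may be concluded. With few subjects enrolled, neither contrast would be well powered, and if both doses work the pooled contrast is the better one. All of this stands. It limits the consequence and rules out an inference a reader might draw, that a live confirmatory test was swapped.

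A second reply concerns two stronger readings. One is that dose gets no comparison at all. The documents do not support it: by-group summaries and a three-arm GST plot with 95% CIs remain, and SAP 10.5 does not expressly confine the t-tests to the pooled contrast. The other is that the change was concealed. It was not: Section 10.5 states the pooling openly, and Protocol Section 8 requires deviations to be described and justified in the clinical study report.

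What these replies leave untouched is narrower. The SAP still names a primary comparison, a significance level and CIs. Its designated list of changes omits the pooling, and 10.5.1 attributes a two-group analysis to a protocol that specifies two dose-level contrasts. Separate CIs for arm means in a plot are not an estimated difference from placebo. Exploratory status makes dose-level estimates with CIs more useful, not less.

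**Conclusion.** The point holds as one of traceability and missing estimates. The SAP departs from the protocol's dose-ordered primary comparison without listing or explaining it, and it specifies no dose-versus-placebo difference with a CI. It does not hold as a claim that a confirmatory result has been compromised.

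The size is conditional. At the planned 25 per arm, and if only one dose has an effect of 0.5 to 1.0 SD, pooling lowers power from 41–93% to 17–52%. If both doses share the effect, pooling raises it (79% to 90% at 0.8 SD). The effect sizes are assumptions, and the planned number was not reached, so the figures show direction and rough scale for the design, not the power of the trial as run. The change is worth making because it costs little and restores the question the protocol asked.

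**What to change.** 1. In the SAP 10.5 t-test tables, which are the analysis planned by default, add rows for 70 mg minus placebo and 40 mg minus placebo with 95% CIs, labelled exploratory, beside the pooled estimate. If the MMRM is run, report the same two differences as contrasts. For GST, use the Appendix 1 scores as derived: the centring cancels in any difference at a visit, and the common divisor keeps the dose-level and pooled differences on one scale.
2. Add a bullet to SAP Section 8 stating that the doses are pooled, that the 70-then-40 order is dropped, and why.
3. Correct the sentence in 10.5.1 so that it no longer presents the two-group analysis as the protocol's.

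The cost is two more rows per table, one bullet and one edited sentence. The dose-level CIs will be wide. In an MMRM with unstructured covariance, a third treatment level adds parameters where the SAP already allows for non-convergence, which is a further reason to place the estimates in the t-test tables first. The exploratory label matters: with a shared placebo arm, testing both doses unadjusted has a simulated one-sided family-wise error of about 4.5%, and about 4.8% with the pooled test added, against 2.5% for the protocol's order.
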